Neuromuscular Weakness (includes myopathy and neuropathy) Specify type, if applicable	Minimal muscle weakness causing no or minimal interference with usual social and functional activities OR No symptoms with decreased strength on examination	Muscle weakness causing greater than minimal interference with usual social and functional activities	Muscle weakness causing inability to perform usual social and functional activities	Disabling muscle weakness causing inability to perform basic self-care functions OR Respiratory muscle weakness impairing ventilation
Neurosensory Alteration (includes paresthesia and painful neuropathy) Specify type, if applicable	Minimal paresthesia causing no or minimal interference with usual social and functional activities OR No symptoms with sensory alteration on examination	Sensory alteration or paresthesia causing greater than minimal interference with usual social and functional activities	Sensory alteration or paresthesia causing inability to perform usual social and functional activities	Disabling sensory alteration or paresthesia causing inability to perform basic self-care functions
Seizures New Onset Seizure ≥18 years of age	NA	NA	1 to 3 seizures	Prolonged and repetitive seizures (eg, status epilepticus) OR Difficult to control (eg, refractory epilepsy)

Neurologic				
Parameter	Grade 1 Mild	Grade 2 Moderate	Grade 3 Severe	Grade 4 Potentially Life-threatening
Pre-existing Seizure	NA	Increased frequency from previous level of control without change in seizure character	Change in seizure character either in duration or quality (eg, severity or focality)	Prolonged and repetitive seizures (eg, status epilepticus) OR Difficult to control (eg, refractory epilepsy)
Syncope	Near syncope without loss of consciousness (eg, presyncope)	Loss of consciousness with no intervention indicated	Loss of consciousness AND Hospitalization or intervention required	NA

Abbreviations: CNS = central nervous system; NA = not applicable.

Pregnancy, Puerperium, and Perinatal				
Parameter	Grade 1 Mild	Grade 2 Moderate	Grade 3 Severe	Grade 4 Potentially Life-threatening
Stillbirth (report using mother's subject ID) Report only one	NA	NA	Fetal death occurring at $\geq 20$ weeks gestation	NA
Preterm Birth (report using mother's subject ID)	Live birth at 34 to $< 37$ weeks gestational age	Live birth at 28 to $< 34$ weeks gestational age	Live birth at 24 to $< 28$ weeks gestational age	Live birth at $< 24$ weeks gestational age
Spontaneous Abortion or Miscarriagef (report using mother's subject ID) Report only one	Chemical pregnancy	Uncomplicated spontaneous abortion or miscarriage	Complicated spontaneous abortion or miscarriage	NA

Abbreviations: ID = identification; NA = not applicable.

f. Definition: A pregnancy loss occurring at  $< 20$  weeks gestational age.

Psychiatric				
Parameter	Grade 1 Mild	Grade 2 Moderate	Grade 3 Severe	Grade 4 Potentially Life-threatening
Insomnia	Mild difficulty falling asleep, staying asleep, or waking up early causing no or minimal interference with usual social and functional activities	Moderate difficulty falling asleep, staying asleep, or waking up early causing more than minimal interference with usual social and functional activities	Severe difficulty falling asleep, staying asleep, or waking up early causing inability to perform usual social and functional activities requiring intervention or hospitalization	NA
Psychiatric Disorders (includes anxiety, depression, mania, and psychosis) Specify disorder	Symptoms with intervention not indicated OR Behavior causing no or minimal interference with usual social and functional activities	Symptoms with intervention indicated OR Behavior causing greater than minimal interference with usual social and functional activities	Symptoms with hospitalization indicated OR Behavior causing inability to perform usual social and functional activities	Threatens harm to self or others OR Acute psychosis OR Behavior causing inability to perform basic self-care functions
Suicidal Ideation or Attempt Report only one	Preoccupied with thoughts of death AND No wish to kill oneself	Preoccupied with thoughts of death AND Wish to kill oneself with no specific plan or intent	Thoughts of killing oneself with partial or complete plans but no attempt to do so OR Hospitalization indicated	Suicide attempted

Abbreviation: NA = not applicable.

Respiratory				
Parameter	Grade 1 Mild	Grade 2 Moderate	Grade 3 Severe	Grade 4 Potentially Life-threatening
Acute Bronchospasm	Forced expiratory volume in 1 second or peak flow reduced to $\geq 70$ to $<80\%$ OR Mild symptoms with intervention not indicated	Forced expiratory volume in 1 second or peak flow 50 to $<70\%$ OR Symptoms with intervention indicated OR Symptoms causing greater than minimal interference with usual social and functional activities	Forced expiratory volume in 1 second or peak flow 25 to $<50\%$ OR Symptoms causing inability to perform usual social and functional activities	Forced expiratory volume in 1 second or peak flow $<25\%$ OR Life-threatening respiratory or hemodynamic compromise OR Intubation
Dyspnea or Respiratory Distress Report only one	Dyspnea on exertion with no or minimal interference with usual social and functional activities OR Wheezing OR Minimal increase in respiratory rate for age	Dyspnea on exertion causing greater than minimal interference with usual social and functional activities OR Nasal flaring OR Intercostal retractions OR Pulse oximetry 90 to $<95\%$	Dyspnea at rest causing inability to perform usual social and functional activities OR Pulse oximetry $<90\%$	Respiratory failure with ventilator support indicated (eg, CPAP, BPAP, intubation)

Abbreviations: CPAP = continuous positive airway pressure, BPAP = bilevel positive airway pressure.

Sensory				
Parameter	Grade 1 Mild	Grade 2 Moderate	Grade 3 Severe	Grade 4 Potentially Life-threatening
Hearing Loss ≥12 years of age	NA	Hearing aid or intervention not indicated	Hearing aid or intervention indicated	Profound bilateral hearing loss (>80 dB at 2 kHz and above) OR Non-serviceable hearing (ie, >50 dB audiogram and <50% speech discrimination)
Tinnitus	Symptoms causing no or minimal interference with usual social and functional activities with intervention not indicated	Symptoms causing greater than minimal interference with usual social and functional activities with intervention indicated	Symptoms causing inability to perform usual social and functional activities	NA
Uveitis	No symptoms AND Detectable on examination	Anterior uveitis with symptoms OR Medical intervention indicated	Posterior or pan-uveitis OR Operative intervention indicated	Disabling visual loss in affected eye(s)
Vertigo	Vertigo causing no or minimal interference with usual social and functional activities	Vertigo causing greater than minimal interference with usual social and functional activities	Vertigo causing inability to perform usual social and functional activities	Disabling vertigo causing inability to perform basic self-care functions
Visual Changes (assessed from Baseline)	Visual changes causing no or minimal interference with usual social and functional activities	Visual changes causing greater than minimal interference with usual social and functional activities	Visual changes causing inability to perform usual social and functional activities	Disabling visual loss in affected eye(s)

Abbreviations: dB = decibel; kHz = kilohertz; NA = not applicable.

Systemic				
Parameter	Grade 1 Mild	Grade 2 Moderate	Grade 3 Severe	Grade 4 Potentially Life-threatening
Acute Allergic Reaction	Localized urticaria (wheals) with no medical intervention indicated	Localized urticaria with intervention indicated OR Mild angioedema with no intervention indicated	Generalized urticaria OR Angioedema with intervention indicated OR Symptoms of mild bronchospasm	Acute anaphylaxis OR Life-threatening bronchospasm OR Laryngeal edema
Chills	Symptoms causing no or minimal interference with usual social and functional activities	Symptoms causing greater than minimal interference with usual social and functional activities	Symptoms causing inability to perform usual social and functional activities	NA
Cytokine Release Syndrome g	Mild signs and symptoms AND Therapy (ie, antibody infusion) interruption not indicated	Therapy (ie, antibody infusion) interruption indicated AND Responds promptly to symptomatic treatment OR Prophylactic medications indicated for $\leq 24$ hours	Prolonged severe signs and symptoms OR Recurrence of symptoms following initial improvement	Life-threatening consequences (eg, requiring pressor or ventilator support)
Fatigue or Malaise Report only one	Symptoms causing no or minimal interference with usual social and functional activities	Symptoms causing greater than minimal interference with usual social and functional activities	Symptoms causing inability to perform usual social and functional activities	Incapacitating symptoms of fatigue or malaise causing inability to perform basic self-care functions
Fever (non-axillary temperatures only)	38.0 to $<38.6^{\circ}\text{C}$ or 100.4 to $<101.5^{\circ}\text{F}$	$\geq 38.6$ to $<39.3^{\circ}\text{C}$ or $\geq 101.5$ to $<102.7^{\circ}\text{F}$	$\geq 39.3$ to $<40.0^{\circ}\text{C}$ or $\geq 102.7$ to $<104.0^{\circ}\text{F}$	$\geq 40.0^{\circ}\text{C}$ or $\geq 104.0^{\circ}\text{F}$
Pain h (not associated with study agent injections and not specified elsewhere) Specify location	Pain causing no or minimal interference with usual social and functional activities	Pain causing greater than minimal interference with usual social and functional activities	Pain causing inability to perform usual social and functional activities	Disabling pain causing inability to perform basic self-care functions OR Hospitalization indicated
Serum Sickness i	Mild signs and symptoms	Moderate signs and symptoms AND Intervention indicated (eg, antihistamines)	Severe signs and symptoms AND Higher level intervention indicated (eg, steroids or IV fluids)	Life-threatening consequences (eg, requiring pressor or ventilator support)
Underweight j >5 to 19 years of age	WHO BMI z-score $<-1$ to $-2$	WHO BMI z-score $<-2$ to $-3$	WHO BMI z-score $<-3$	WHO BMI z-score $<-3$ with life-threatening consequences
Unintentional Weight Loss (excludes postpartum weight loss)	NA	5 to $<9\%$ loss in body weight from Baseline	$\geq 9$ to $<20\%$ loss in body weight from Baseline	$\geq 20\%$ loss in body weight from Baseline OR Aggressive intervention indicated (eg, tube feeding, total parenteral nutrition)

Abbreviations: BMI = body mass index; IV = intravenous; NA = not applicable; WHO = World Health Organization.

g. Definition: A disorder characterized by nausea, headache, tachycardia, hypotension, rash, and/or shortness of breath.

h. For pain associated with injections or infusions, see the *Site Reactions to Injections and Infusions* section.

i. Definition: A disorder characterized by fever, arthralgia, myalgia, skin eruptions, lymphadenopathy, marked discomfort, and/or dyspnea.

j. WHO reference tables for subjects  $>5$  to 19 years of age may be accessed at the following URL: [http://www.who.int/growthref/who2007\\_bmi\\_for\\_age/en/](http://www.who.int/growthref/who2007_bmi_for_age/en/).

Urinary				
Parameter	Grade 1 Mild	Grade 2 Moderate	Grade 3 Severe	Grade 4 Potentially Life-threatening
Urinary Tract Obstruction	NA	Signs or symptoms of urinary tract obstruction without hydronephrosis or renal dysfunction	Signs or symptoms of urinary tract obstruction with hydronephrosis or renal dysfunction	Obstruction causing life-threatening consequences

Abbreviation: NA = not applicable.

Laboratory Values k: Chemistries				
Parameter	Grade 1 Mild	Grade 2 Moderate	Grade 3 Severe	Grade 4 Potentially Life-threatening
Acidosis	NA	pH $\geq$ 7.3 to <LLN	pH <7.3 without life-threatening consequences	pH <7.3 with life-threatening consequences
Albumin, Low (g/dL; g/L)	3.0 to <LLN 30 to <LLN	$\geq$ 2.0 to <3.0 $\geq$ 20 to <30	<2.0 <20	NA
Alkaline Phosphatase, High	1.25 to <2.5 $\times$ ULN	2.5 to <5.0 $\times$ ULN	5.0 to <10.0 $\times$ ULN	$\geq$ 10.0 $\times$ ULN
Alkalosis	NA	pH >ULN to $\leq$ 7.5	pH >7.5 without life-threatening consequences	pH >7.5 with life-threatening consequences
ALT or SGPT, High Report only one	1.25 to <2.5 $\times$ ULN	2.5 to <5.0 $\times$ ULN	5.0 to <10.0 $\times$ ULN	$\geq$ 10.0 $\times$ ULN
Amylase (Pancreatic) or Amylase (Total), High Report only one	1.1 to <1.5 $\times$ ULN	1.5 to <3.0 $\times$ ULN	3.0 to <5.0 $\times$ ULN	$\geq$ 5.0 $\times$ ULN
AST or SGOT, High Report only one	1.25 to <2.5 $\times$ ULN	2.5 to <5.0 $\times$ ULN	5.0 to <10.0 $\times$ ULN	$\geq$ 10.0 $\times$ ULN
Bicarbonate, Low (mEq/L; mmol/L)	16.0 to <LLN 16.0 to <LLN	11.0 to <16.0 11.0 to <16.0	8.0 to <11.0 8.0 to <11.0	<8.0 <8.0
Bilirubin Direct Bilirubin, High	NA	NA	>ULN with other signs and symptoms of hepatotoxicity	>ULN with life-threatening consequences (eg, signs and symptoms of liver failure)
Total Bilirubin, High	1.1 to <1.6 $\times$ ULN	1.6 to <2.6 $\times$ ULN	2.6 to <5.0 $\times$ ULN	$\geq$ 5.0 $\times$ ULN
Calcium, High (mg/dL; mmol/L)	10.6 to <11.5 2.65 to <2.88	11.5 to <12.5 2.88 to <3.13	12.5 to <13.5 3.13 to <3.38	$\geq$ 13.5 $\geq$ 3.38
Calcium (Ionized), High (mg/dL; mmol/L)	>ULN to <6.0 >ULN to <1.5	6.0 to <6.4 1.5 to <1.6	6.4 to <7.2 1.6 to <1.8	$\geq$ 7.2 $\geq$ 1.8
Calcium, Low (mg/dL; mmol/L)	7.8 to <8.4 1.95 to <2.10	7.0 to <7.8 1.75 to <1.95	6.1 to <7.0 1.53 to <1.75	<6.1 <1.53
Calcium (Ionized), Low (mg/dL; mmol/L)	<LLN to 4.0 <LLN to 1.0	3.6 to <4.0 0.9 to <1.0	3.2 to <3.6 0.8 to <0.9	<3.2 <0.8
Cardiac Troponin I, High	NA	NA	NA	Levels consistent with myocardial infarction or unstable angina as defined by the local laboratory
Creatine Kinase, High	3 to <6 $\times$ ULN	6 to <10 $\times$ ULN	10 to <20 $\times$ ULN	$\geq$ 20 $\times$ ULN
Creatinine, High Report only one	1.1 to 1.3 $\times$ ULN	>1.3 to 1.8 $\times$ ULN OR Increase to 1.3 to <1.5 $\times$ subject's Baseline	>1.8 to <3.5 $\times$ ULN OR Increase to 1.5 to <2.0 $\times$ subject's Baseline	$\geq$ 3.5 $\times$ ULN OR Increase of $\geq$ 2.0 $\times$ subject's Baseline

## Laboratory Values k: Chemistries

Parameter	Grade 1 Mild	Grade 2 Moderate	Grade 3 Severe	Grade 4 Potentially Life-threatening
Creatinine Clearance l,m or eGFR, Low Report only one	NA	<90 to 60 mL/min or mL/min/1.73 m  OR 10 to <30% decrease from subject's Baseline	<60 to 30 mL/min or mL/min/1.73 m  OR 30 to <50% decrease from subject's Baseline	<30 mL/min or mL/min/1.73 m  OR ≥50% decrease from subject's Baseline or dialysis needed
Glucose (mg/dL; mmol/L) Fasting, High	110 to 125 6.11 to <6.95	>125 to 250 6.95 to <13.89	>250 to 500 13.89 to <27.75	≥500 ≥27.75
Nonfasting, High	116 to 160 6.44 to <8.89	>160 to 250 8.89 to <13.89	>250 to 500 13.89 to <27.75	≥500 ≥27.75
Glucose, Low (mg/dL; mmol/L)	55 to 64 3.05 to <3.55	40 to <55 2.22 to <3.05	30 to <40 1.67 to <2.22	<30 <1.67
Lactate, High	ULN to <2.0 × ULN without acidosis	≥2.0 × ULN without acidosis	Increased lactate with pH <7.3 without life-threatening consequences	Increased lactate with pH <7.3 with life-threatening consequences
Lipase, High	1.1 to <1.5 × ULN	1.5 to <3.0 × ULN	3.0 to <5.0 × ULN	≥5.0 × ULN
Lipid Disorders (mg/dL; mmol/L)				
Cholesterol, Fasting, High ≥18 years of age	200 to <240 5.18 to <6.19	240 to <300 6.19 to <7.77	≥300 ≥7.77	NA
LDL, Fasting, High ≥18 years of age	130 to <160 3.37 to <4.12	160 to <190 4.12 to <4.90	≥190 ≥4.90	NA
Triglycerides, Fasting, High	150 to 300 1.71 to 3.42	>300 to 500 >3.42 to 5.7	>500 to <1,000 >5.7 to 11.4	>1,000 >11.4
Magnesium n, Low (mEq/L; mmol/L)	1.2 to <1.4 0.60 to <0.70	0.9 to <1.2 0.45 to <0.60	0.6 to <0.9 0.30 to <0.45	<0.6 <0.30
Phosphate, Low (mg/dL; mmol/L)	2.0 to <LLN 0.65 to <LLN	1.4 to <2.0 0.45 to <0.65	1.0 to <1.4 0.32 to <0.45	<1.0 <0.32
Potassium, High (mEq/L; mmol/L)	5.6 to <6.0 5.6 to <6.0	6.0 to <6.5 6.0 to <6.5	6.5 to <7.0 6.5 to <7.0	≥7.0 ≥7.0
Potassium, Low (mEq/L; mmol/L)	3.0 to <3.4 3.0 to <3.4	2.5 to <3.0 2.5 to <3.0	2.0 to <2.5 2.0 to <2.5	<2.0 <2.0
Sodium, High (mEq/L; mmol/L)	146 to <150 146 to <150	150 to <154 150 to <154	154 to <160 154 to <160	≥160 ≥160
Sodium, Low mEq/L; mmol/L)	130 to <135 130 to <135	125 to <130 125 to <130	121 to <125 121 to <125	≤120 ≤120
Uric Acid, High (mg/dL; mmol/L)	7.5 to <10.0 0.45 to <0.59	10.0 to <12.0 0.59 to <0.71	12.0 to <15.0 0.71 to <0.89	≥15.0 ≥0.89

Abbreviations; ALT = alanine aminotransferase; AST = aspartate aminotransferase; eGFR = estimated glomerular filtration rate; LDL = low-density lipoprotein; LLN = lower limit of normal; NA = not applicable; SGOT = serum glutamic oxaloacetic transaminase; SGPT = serum glutamic pyruvic transaminase; ULN = upper limit of normal.

k. Reminder: An asymptomatic abnormal laboratory finding without an accompanying adverse event should not be reported to DAIDS in an expedited time frame unless it meets protocol-specific reporting requirements.

l. Reminder: Choose the method that selects for the higher grade.

- m. Use the applicable formula (ie, Cockcroft-Gault in mL/min or Schwartz, MDRD, CKD-Epi in mL/min/1.73m^2). Sites should choose the method defined in their study and when not specified, use the method most relevant to the study population.
- n. To convert a magnesium value from mg/dL to mmol/L, laboratories should multiply by 0.4114.

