10. History of malignancy other than HCC unless the subject's malignancy has been in complete remission off chemotherapy and without additional medical or surgical interventions during the 3 years before Screening

11. History or presence at Screening of electrocardiogram (ECG) abnormalities deemed clinically significant, in the opinion of the Investigator
12. History of hypersensitivity or idiosyncratic reaction to any components or excipients of the investigational drug
13. History of any significant food or drug-related allergic reactions such as, anaphylaxis or Stevens-Johnson syndrome
14. The following exclusionary laboratory results at Screening:
  - Hemoglobin <12g/dL for males or <11g/dL for females
  - Platelet count <100,000/mm^3
  - White blood cell count <2,500/mm^3
  - Absolute neutrophil count <1,500/mm^3
  - Albumin <lower limit of normal
  - History of thyroid disease poorly controlled on prescribed medications, with thyroid-stimulating hormone (TSH), free triiodothyronine or free thyroxine (T4) outside the normal limits
  - Total bilirubin >1.2 × ULN unless known Gilbert's syndrome; subjects with Gilbert's syndrome are eligible for study participation if the direct bilirubin is within the normal range
  - Direct bilirubin >1.2 × ULN
  - ALT ≤1 × ULN or ≥10 × ULN
  - Serum alpha fetoprotein (AFP) ≥100 ng/mL. If AFP at Screening is > ULN but <100 ng/mL, the subject is eligible if hepatic imaging prior to initiation of study drug reveals no lesions indicative of possible HCC
  - International Normalized Ratio (INR) >1.5 × ULN (unless on a stable anticoagulant regimen)
  - Glomerular filtration rate <60 mL/min/1.73 m^2 by Chronic Kidney Disease Epidemiology Collaboration equation ([Levey et al 2009](#))
  - Serum creatinine >1.5 × ULN
  - Any other laboratory abnormality deemed clinically significant by the Sponsor or the Investigator
15. Subjects receiving prohibited concomitant medications or medications that should be avoided (as outlined in [Section 6.6](#) and [Appendix 5](#)) within 7 days or 5 half-lives (if known), whichever is longer, prior to administration of the first dose of study drug (Day 1) and for the duration of the study period. Please refer to Exclusion Criterion #1 for criteria regarding liver protecting and/or ALT lowering agents

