#### **7.2.1.1.      Treatment-Emergent Laboratory Abnormalities**

Treatment-emergent laboratory abnormalities are defined as values that increase at least 1 toxicity grade from Baseline at any postbaseline time point, up to and including the date of last dose of any study drug plus 28 days for the Overall Treatment Phase. For the Randomized Treatment Phase, the treatment-emergent laboratory abnormalities will be summarized up to the last dose at Week 24.

If the relevant baseline laboratory value is missing, any abnormality of at least Grade 1 observed within the time frame specified above will be considered treatment emergent.

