### 7.2.1.2. Summaries of Laboratory Abnormalities

A summary (number and percentage of subjects) for treatment-emergent laboratory abnormalities will be provided by lab test and treatment group; subjects will be categorized according to the most severe postbaseline abnormality grade for a given lab test.

For all summaries of laboratory abnormalities, the denominator is the number of subjects with nonmissing postbaseline values up to 28 days after last dose date for the Overall Treatment Phase and up to Week 24 dose date for the Randomized Treatment Phase.

The maximum postbaseline grade observed up to 28 days after last dose date or the Week 24 dose date will be tabulated for each laboratory test, and percentages will be based on the number of subjects with a postbaseline evaluation of the specific laboratory test. The laboratory abnormalities during the Follow-up Phase will also be summarized.

A by-subject listing of graded laboratory abnormalities will be provided by subject number and visit in chronological order. This listing will include all test results that were collected throughout the study for the lab test of interest, with all applicable severity grades displayed.

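### For subjects with Baseline eGFR of about 67 to 89, the treatment-emergent table misses falls of 10 to <30% that stay at or above 60, yet it counts a change from 91 to 89 as a new Grade 2

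*Combined protocol and SAP*

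**What the plan says.** The row for creatinine clearance "or eGFR, Low Report only one" in protocol Appendix 3 (Laboratory Values: Chemistries) has NA under Grade 1. Grade 2 is "<90 to 60 mL/min or mL/min/1.73 m"² or a relative fall, "OR 10 to <30% decrease from subject's Baseline". Grade 3 is "<60 to 30 mL/min or mL/min/1.73 m"² or "30 to <50% decrease from subject's Baseline". Grade 4 is below 30, a fall of 50% or more, or dialysis. Footnote l says that whichever method yields the higher grade applies.

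Protocol 5.3, criterion 14, excludes "Glomerular filtration rate <60 mL/min/1.73 m"² at Screening, so subjects at 60 to 89 may enroll.

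The SAP grades laboratory results by Appendix 3 (7.2.1) and has no separate rule for eGFR. SAP 7.2.1.1 defines treatment-emergent abnormalities as "values that increase at least 1 toxicity grade from Baseline at any postbaseline time point". In SAP 7.2.1.2, "subjects will be categorized according to the most severe postbaseline abnormality grade for a given lab test", and the maximum postbaseline grade is also tabulated for each test. Neither document says what to do when a Baseline eGFR already meets the absolute limb.

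**The concern.** At Baseline the change is zero, so only the absolute limb can set the Baseline grade. Anyone at 60 to 89 starts at Grade 2. The Grade 2 relative limb, which is there to pick up a change within a subject, cannot then raise the grade, and the rule of a one-grade rise discards the fall. A subject just above 90 has the opposite problem: a trivial change crosses 90 and, with no Grade 1 to pass through, goes straight from no grade to Grade 2.

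The proportion with abnormal laboratory results is part of the primary endpoint (protocol 3.2.1), and the graded tables are where that proportion is reported. With about 20 subjects per arm and no stratification on renal function, a chance difference between arms in entry eGFR around 90 would shift the treatment-emergent count for reasons unrelated to treatment.

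**Working it through.** **Rule as coded.** Grade = the higher of the absolute-limb and relative-limb grades (Appendix 3, footnote l). Treatment-emergent = postbaseline grade at least Baseline grade + 1 (SAP 7.2.1.1). Percent fall = 100 × (Baseline − value) / Baseline. The plan gives no figure of its own to reproduce.

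**Worked cases.**

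| Baseline | Worst value | Fall | Baseline grade | Worst grade | Counted? |
|---|---|---|---|---|---|
| 91 | 89 | 2/91 = 2.2% | none | 2 (absolute) | yes |
| 120 | 109 | 11/120 = 9.2% | none | none | no |
| 88 | 62 | 26/88 = 29.5% | 2 | 2 | no |
| 80 | 60 | 20/80 = 25.0% | 2 | 2 | no |
| 70 | 60 | 10/70 = 14.3% | 2 | 2 | no |
| 89 | 62 | 27/89 = 30.3% | 2 | 3 (relative) | yes |
| 70 | 59 | 11/70 = 15.7% | 2 | 3 (absolute) | yes |
| 60 | 59 | 1/60 = 1.7% | 2 | 3 (absolute) | yes |

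**Limits of the missed zone.** A fall is missed when it is 10 to <30% and ends at 60 or above.
- A 10% fall can end at 60 or above only if Baseline is at least 60/0.9 = 66.7. Below that, every fall of 10% or more ends under 60 and counts as Grade 3 or higher.
- The 30% limit is reached before the 60 limit only if Baseline exceeds 60/0.7 = 85.7. Between 66.7 and 85.7, crossing 60 is what makes a fall count.
- So the affected Baselines are about 67 to 89.

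**Maximum-grade table.** A stable 75 and a fall from 88 to 66 (25%) both show Grade 2, so the table cannot separate them.

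**Size, by simulation.** The documents give no eGFR distribution, so these inputs are assumptions: entry eGFR normal with mean 105 and SD 15, values below 60 excluded, log-normal within-subject error with CV 3 to 7%. The worst of the 7 chemistry visits to Week 24 (Weeks 2, 4, 8, 12, 16, 20, 24) is compared with Baseline.

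| Scenario | Entering ≥90 | 75–89 | 60–74 |
|---|---|---|---|
| True 15% fall, CV 3–5% | about 99% flagged | 1–5% | about 70% |

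With no true change, 11%, 36% and 55% of those entering at 90 or above are flagged at CV 3%, 5% and 7%, against 1 to 2% of those entering below 90. With an assumed mean of 95, the contrast under a 15% fall persists: over 99% at 90 or above, against about 2 to 8% at 75 to 89 (CV 3 to 5%).

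About 16 to 17% of simulated subjects enter below 90 at CV 3 to 5%. That is about 3 of 20 per arm (0.16 × 20 = 3.2; 0.17 × 20 = 3.4).

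**The case against.** Several points on the other side stand.

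- **Larger falls count.** A reader might infer that no real fall can register in anyone entering at 60 to 89. The Appendix 3 row does not support that: a fall of 30% or more, or to below 60, is Grade 3 or higher and is treatment-emergent.
- **The missing Grade 1 is not the cause.** The absolute limb sets the Baseline grade to 2, and the one-grade rule does the rest. The missing Grade 1 only explains why 91 to 89 enters directly at Grade 2.
- **The falls are visible elsewhere.** Protocol 10.3.6.2 summarizes values and change from Baseline by visit. SAP 7.2 provides quantitative summaries, and the SAP 7.2.1.2 listing shows all results with their grades. The creatinine row has its own relative limb from 1.3 × Baseline. If eGFR moved in inverse proportion to creatinine (an assumption), that would be a fall of about 1 − 1/1.3 = 23%, so it recovers only part of the zone.
- **A strong group effect would still show.** Under the assumed 15% fall, about 85% of all subjects are flagged, against about 10 to 30% with no change (CV 3 to 5%). The documents do not support reading this as a hidden renal effect.
- **Much of the noise comes from the relative limb.** With no true change, the 10% limb alone flags about 4%, 28% and 49% of those entering at 90 or above (CV 3%, 5%, 7%). At CV 5 to 7% the absolute limb adds only 6 to 7 points.
- **Context.** The scale is adapted from the DAIDS table, and any test with a nonzero Baseline grade has some version of this problem. The analysis is descriptive, in a terminated study reported in a synoptic CSR.

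One further qualification: the exclusion applies at Screening, whereas Baseline is the last value on or before first dose. An occasional Baseline below 60 is therefore possible.

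None of this restores the missed falls to the treatment-emergent table.

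**Conclusion.** The point holds as a minor fault in the graded tables. For Baselines of about 67 to 89, a fall of 10 to <30% that ends at 60 or above is never treatment-emergent, while a 2.2% change across 90 is. The maximum-grade table cannot tell a stable value of 60 to 89 from a fall within that range. This follows from the text alone. It is an interaction between the adapted scale and the SAP's one-grade rule, not a contradiction between documents.

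The detection rates rest on the assumed entry distribution and CV and should be read as illustrative. The actual number of subjects affected cannot be computed from the documents. At the assumed values it would be at most a few per arm.

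**What to change.** In SAP 7.2.1.1 and 7.2.1.2, keep the grade-shift table and add two items for eGFR:

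1. The number and percentage of subjects by worst percent decrease from Baseline (10 to <30%, 30 to <50%, ≥50%), counted whatever the Baseline grade.
2. A shift table of Baseline category by worst postbaseline category (≥90, 60–89, 30–59, <30).

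Under the same assumptions, the percent-decrease count detects a true 15% fall in about 97 to 99% of subjects entering at 75 to 89 (CV 5% and 3%), instead of 1 to 5%.

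The cost is one extra count and one extra table, from data already in the chemistry panel. The downside is noise. With no true change, the percent-decrease count flags about 2%, 15% and 26% of subjects entering below 90 at CV 3%, 5% and 7%, against 1 to 2% under the current rule. It does not remove most of the noise at 90 or above either. For these reasons it should supplement the grade-shift table, not replace it.
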